C3.1 Methodological issues to be addressed in de-implementation pilots A well-designed pilot study has many purposes, including testing methods of recruitment; selecting the most appropriate primary outcome; testing acceptability of the intervention by stakeholders; ironing out feasibility and fidelity issues; refining the full study protocol; and estimating sample size for a full trial.^{45,95} As highlighted in implementation literature, preparation and planning are central to successful intervention development and implementation. The need for clear outcomes (e.g., castration rate), systematic, theory-based interventions to change provider behavior, and a timetable are necessary to successfully set up our full-scale evaluation trial. Further refinement in the pilot work will allow us to explore outcomes including the total number of ADT injections as we will also be working to stop treatment with low-value ADT. As illustrated in Table 3 below, the piloting of the intervention strategies will focus on 4 major methodological issues.⁴⁵ We will examine issues surrounding recruitment, acceptability, feasibility, scalability, and data collection for the full-scale trial.

Table 3. Methodological issues requiring pilot evaluation prior to a full-scale de-implementation trial

Issue	Assessment	Potential outcome
Recruitment randomization scalability	Monitor proposed recruitment strategy at each facility; check practicality of cluster randomization of facilities; identify issues of participation refusal or withdrawal; acceptability of randomization; number of eligible participants per month; compare clinic flow across recruitment strategies	Select most effective recruitment and randomization strategy; trial messaging to sites; discern patient, provider and cluster sample sizes; refining eligibility screening
Acceptability of intervention	Check acceptability of interventions with ADT prescribers and clinic staff at pilot sites; settings for each intervention; consent and documentation practices; tailoring strategies are acceptable; timing of intervention relative to visit	Identify acceptable components of each intervention in clinical practice; consent processes; efficient documentation practices
Feasibility in clinical practice	Assess burden on clinic staff and providers to participate; monitor clinical time and workflow; assess adherence to intervention; technical performance of EMR-based intervention(s); participants representative of those expected in full-scale trial; intervention fidelity	Time and resources needed to roll out in randomized sites; learn research and clinic administrative staff roles for trial; standardization; scheduling practices
Data collection and outcome assessment	Monitor follow up practices for patients on ADT; monitor for asymmetric attrition/retention across intervention sites; missing data; review choice of primary outcome, study design; effect variability	Willingness to participate by intervention preference; effect size; consider hybrid study; duration; full-scale protocol

C3.2 Study populations

We will conduct pilot testing at 4 sites with multi-disciplinary review by study team members to confirm target clinic visits prior to engagement with site provider. [name] (Co-PI) will lead the pilot efforts at the VA Ann Arbor Urology Clinic with [name] leading pilot efforts at the VA Ann Arbor Urologic Oncology clinic and [name] leading the efforts in the VA Ann Arbor Radiation Oncology clinic. Drs. [name], and [name], each with urologic oncology practices, will lead pilot efforts at their respective VA sites (Greater LA and NY Harbor). The number of patients receiving primary ADT for localized prostate cancer and receiving ADT for non-metastatic biochemical recurrence with low PSA levels at each site should be adequate for piloting based on preliminary data. However, the primary purpose of the pilot is to assess for

issues in the implementation process in order to further refine the intervention plan. The pilot testing will play a critical role to help us understand the acceptability, feasibility, and scalability of these strategies in order to conduct the full-scale pilot randomized implementation trial. In particular, we expect to learn best practices in introducing both strategies to sites in the most efficient, least intrusive ways.

For the 4-site pilot randomized implementation trial, we will recruit sites from the VA facilities with the highest levels of low-value ADT use. We will target facilities with high rates of low-value ADT for localized prostate cancer and non-metastatic biochemical recurrence. Sites will be identified through a combination of CDW data pulls and chart reviews, with expert multi-disciplinary review by study team members prior to moving forward with site providers. We will also match our 4 intervention sites with up to 8 control sites acting as contemporary controls for ADT overuse and our effectiveness outcomes.

C3.3 Data sources and analysis

We anticipate conducting the pilots for six months. For the pilot, our research team will host regular calls between Drs. [name] (Co-PI), [name] (Co-I), [name] (Consultant), [name] (Consultant), [name] (Consultant), the Ann Arbor project team, other Co-I's and consultants to discuss issues. We will take notes during these calls. At the beginning, we anticipate calls will occur weekly to deal with barriers and complications. By the end of the interventions, we anticipate that calls will be shorter and less frequent, and will focus more on achievements and lessons learned regarding methodological issues as we prepare for the pilot randomized implementation trial. We will extract data on ADT use from VA and Medicare data to remain informed and updated about the status of chemical castration as primary treatment and treatment for non-metastatic biochemical recurrence across VA (including the pilot sites). This will allow us to monitor secular trends in performance and assess possible changes in chemical castration over the pilot period in our pilot sites. We will collect and maintain descriptive data, which is most appropriate for pilot studies.⁹⁵ We will use content analysis methods to assess key issues arising from conference call field notes. We will use bivariate analyses (t-test or chi-squared test) to assess the parameters (central tendency and variation) for pilot intervention variables including patient and provider demographics.⁹⁰ In preparation for our pilot randomized implementation trial, we will use national VA data to identify potential sites. Data collection and analysis procedures will be further refined during the pilot.

D. Human Subjects

D1. Risk to subjects

D1.1 Human subject involvement and characteristics

Prior to commencement of study activities, we will obtain VA Ann Arbor Institutional Review Board approval, requesting exemption under categories 2 (survey), 3 (benign behavioral interventions), and 4 (secondary data analysis). As an exempt project, all project modifications will be submitted to the VA Ann Arbor Research & Development Committee for approval.

We will conduct pilot testing among clinicians who prescribe ADT at VA Ann Arbor Healthcare System, VA Greater Los Angeles Healthcare System, and VA NY Harbor Healthcare System. Drs. [name] (Co-PI), [name] (Co-I), [name] (Consultant), [name] (Consultant), and [name] (Consultant) will serve as champions for the pilot sites, working with the Ann Arbor project team to help with implementation. This includes providing information on site workflow, regular status updates, and feedback on implementation. For the pilot randomized implementation trial, the study team will recruit Site Champions (e.g., Urology Chiefs) at each of the participating sites. All clinicians who prescribe ADT at participating sites will be eligible to receive the interventions. Ann Arbor team members will send clinicians an email with an attached Research Information Sheet providing an opportunity to opt out of participation. Opting out means that they will not be asked to participate in surveys or other approaches to measuring provider responses and the interventions will not be triggered for any of their patients or clinic visits.

No other inclusion or exclusion criteria will be applied. No patients will be recruited for either the pilot testing or pilot randomized implementation trial; however, identifiable data will be collected from national VA CDW, Central Cancer Registry, Vital Status, and CMS data, and chart reviews will be conducted using CPRS/Capri/JLV/ WebVRAM, to identify target clinic visits and assess outcomes. Identifiers will be stripped as early as possible, once analytic data sets are created.

D1.2 Sources of materials

As part of our development efforts, we have created real-time ‘smart’ criteria to support streamlined implementation. We will collect data using CDW/Cancer Registry/Vital Status/CMS data from October 1, 1999 to June 30, 2024 on up to 100,000 patients to identify low value ADT use at pilot testing sites and to determine eligibility of implementation trial sites. While the cohort will be defined using 2020 – 2022 data, the remaining data is needed to properly identify target clinic visits and ensure the alert criteria (e.g., prior ADT injections) triggers are acceptable to providers. We will develop and test the intervention strategies focusing on major methodological issues including: provider engagement, acceptability, feasibility, scalability, and data collection for the full-scale trial. [name] (Co-PI) and the research team, with the support of weekly study team meetings, will be responsible for each pilot assessment and provider engagement. There will be regular calls between [name] (Co-PI), the pilot Site Champions/Study Consultants, the Ann Arbor project team, Co-Is and consultants to discuss common issues or concerns during the pilot. We will take field notes during these calls. At the beginning, we anticipate the calls will occur weekly and deal with barriers and complications. By the end of the intervention, we anticipate that calls will be shorter and less frequent, and will focus more on achievements and lessons learned regarding methodological issues as we prepare for the randomized evaluation trial. We will extract data on ADT use from VA and Medicare data to remain informed about the status of chemical castration as primary treatment for localized prostate cancer and treatment for non-metastatic biochemical recurrence across VA (including pilot sites). This will allow us to monitor secular trends in performance over this period, and to assess possible changes in chemical castration over the pilot period. We will collect and maintain descriptive data, which is most appropriate for pilot studies. We will use content analysis methods to assess issues arising in each site from the conference call field notes. All data will be collected specifically for the purposes of proposed research.

Table. D1.2 Sources of Materials

Pilot		
Engagement, randomization, Scalability	Monitor proposed engagement strategy at each facility; check practicality of cluster randomization of facilities; identify issues of participation refusal or withdrawal; number of eligible clinic visits per month; compare clinic flow across engagement strategies.	Select most effective engagement and randomization strategy; messaging of trial to potential sites; discern patient, provider and cluster sample sizes; eligibility screening refinement
Acceptability of intervention	Check acceptability of interventions with providers clinic staff at pilot sites; settings for each intervention; documentation practices; tailoring strategies acceptable; timing of intervention relative to visit	Identify acceptable components of each intervention in clinical practice; efficient documentation practices
Feasibility in clinical practice	Assess burden on clinic staff and providers to participate; monitor clinical time and workflow; assess adherence to intervention; technical performance of EMR-based intervention(s); participants representative of those expected in full-scale trial; fidelity to each intervention;	Time and resources needed to roll out in randomized sites; learn research and clinic administrative staff roles necessary for trial; standardization of intervention; identify scheduling practices
Data collection and outcome assessment	monitor for asymmetric attrition/retention across intervention sites; missing data; review choice of primary outcome, study design; variability in effects	Willingness to participate may depend on intervention preference; estimates of effect size; consider hybrid study; duration; full-scale protocol

D1.3 Potential risks

Risks for participating providers include possible slight disruption of clinical workflow and a low likelihood of psychological distress. These risks will be site- and intervention-dependent. We are requesting exemption under categories 2 (survey), 3 (benign behavioral interventions), and 4 (secondary data analysis). Providers will be emailed a Research Information Sheet with details of the study. The right of providers to discontinue their involvement in the research at any time will be fully disclosed in the Information Sheet. We are also requesting a waiver of HIPAA authorization for access to PHI. The proposed research qualifies for this waiver because it involves no more than minimal risk to subjects and the waiver will not adversely affect the rights or welfare of subjects. In addition, the research could not practicably be carried out without the waiver. In order to be granted the waiver, we demonstrate procedures (outlined below) that protect patient identifiers from improper use and disclosure.

The investigative team has considerable experience in maintaining the confidentiality of large datasets and has established procedures in place to ensure data confidentiality. All investigators and research staff will have met training requirements for handling protected health information as defined by the Health Insurance Portability and Accountability Act (HIPAA), data security, and privacy. All data storage and handling will follow defined protocols at the VA Ann Arbor Healthcare System. All data collected from VA CDW/Cancer Registry/Vital Status/CMS records and CPRS/Capri/JLV/ WebVRAM will reside on VINCI and in an access-restricted study folder on the AAVA OI&T secure drive. Paper records created for chart review purposes will be labeled with a study ID only and stored in locked filing cabinets in the locked 3rd floor CCMR suite in VA-rented space at NCRC. Once data is digitized, the paper copies will be placed in the VA's secure shredder bin. Survey data will be collected anonymously in VA Qualtrics and downloaded into the access-restricted study folder for additional analyses.

D2. Adequacy of protection from risk

D2.1 Recruitment and informed consent

Providers, service leadership, and staff involved with ADT prescribing at the participating sites will be given an overview of the site-specific intervention, highlighting the nature and purpose of the proposed research, as well as what they should expect to encounter during routine clinical care should they agree to proceed with the study. Providers will be sent an email with a Research Information Sheet (attachment) attached informing them of their ability to opt out and inviting them to the Implementation Education Session (IES) (attachment).

D2.2 Protection against risk

All study staff will have met local training requirements for handling protected health information. All data will be stored on VINCI and in an access-restricted study folder on a secure server at the Ann Arbor VA, or in VA Qualtrics, accessible only by authorized study team members. Individual real social security numbers (SSNs) will be needed to link individual data across data sources (e.g., CDW-Oncology to clinical data) and to conduct chart reviews. An electronic cross-walk file will be used when accessing large datasets for analyses. Access to the cross-walk file will be restricted to authorized personnel, who have met the security criteria necessary for access to patient identifier mapping files at the VA's Austin Automation Center. As VA employees, all study staff members are subject to the Federal Privacy Act. Site Champions will not use coercion in their role and will not be privy to names of providers opting out of the research.

D3. Potential benefits of the proposed research to the subject and others

Though participation in the research study may not directly benefit participants, the data collected will benefit future providers and patients by improving the quality of prostate cancer care in and eventually outside the VA through theory-based interventions to reduce low value cancer care. Due to the expanding population of aging men with prostate cancer, enhancing safety by promoting evidence-based use of chemical castration promotes quality care and likely will improve quality of life. It is possible that providers taking part in the interventions will gain knowledge about better use of chemical castration for prostate cancer patients, particularly with respect to localized disease and non-metastatic biochemical recurrence. Moreover, understanding how providers unlearn ineffective clinical behaviors is a critical step towards optimizing cancer care and de-implementation of low value services. Unlearning clinical behaviors such as prescribing ADT in low evidence settings can have substantial benefits. First, patients are no longer subjected to treatment harms with little to no benefit. Second, unlearning misaligned castration practices can provide opportunity for more efficient, higher value use of specialty care providers. Last, acquiring the skill of unlearning can increase flexibility and willingness to adapt to evidence more proactively. The risks posed to research participants are minimal, consisting of potential

breaches in confidentiality. We believe we have procedures in place that will minimize these risks, and that the overall project has a highly favorable risk:benefit ratio.

D4. Importance of knowledge to be gained

Many men with prostate cancer are castrated with long-acting injectable drugs (i.e., androgen deprivation therapy or ADT). Although some patients benefit, it is also used in patients with little or nothing to gain. The best ways to stop, or de-implement, low value cancer care are unknown. A significant scientific and clinical knowledge gap remains in prioritizing which barriers to stopping castration in low value settings need to be targeted for effective de-implementation. We will compare two different approaches for reducing low value ADT use. In doing so, this study will address important issues surrounding provider behavior change and serve as a model to decrease overtreatment more broadly. This is especially important given *Choosing Wisely* and the need for effective de-implementation strategies. Throughout this study, we will keep a broad focus so that our work lays a foundation for transforming how and why castration is performed for prostate cancer treatment across the globe. This work will address provider preferences and concerns through pilot tailoring and advance de-implementation science for low value care through our subsequent de-implementation evaluation trial.

D5. Data Safety and Monitoring Plan

Drs. [name] (PI) and [name] (Co-PI) will be responsible for reporting all adverse events that might arise during the course of the study to the Ann Arbor Veterans Affairs Health System IRB as well as to the ISSO and PO as appropriate. Adverse events during this study would likely consist only of breaches in confidentiality. As outlined above, precautions have been taken to prevent this. However, should such breaches occur, Drs. [name] (PI) and [name] (Co-PI) will report these occurrences to the overseeing IRBs as well as the ISSO and PO within 48 hours of discovery.

D6. Inclusion of Women and Minorities

For provider recruitment, no exclusions will be made on the basis of gender, race or ethnicity. The only eligibility requirement is that participants be providers with experience caring for prostate cancer patients on ADT.

References

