All 3 pilot test sites will be followed for up to 6 months. To implement the interventions and assess for issues in the implementation process in order to further refine the intervention plan, information will be collected regarding the process of ADT ordering at each site, including who is involved, through conversations with the Site Champion (who is also a project consultant) or their designee. Additionally, information regarding implementation status as well as any changes in site processes around prescribing ADT will be discussed at regular team meetings with the project consultants (including Site Champions). For both the pilot and implementation trial, outcomes will be collected from VA CDW/Cancer Registry/Vital Status/CMS records and CPRS/Capri/JLV/WebVRAM for all clinic visits documented as providing low-value ADT at baseline, 3 and 6 months. An organizational survey will be developed and refined throughout the pilot. For the pilot implementation trial, an anonymous clinic assessment survey will be administered to Site Champions at baseline and an ADT provider assessment will be administered to participating site providers at baseline and 1-month post-intervention through VA Qualtrics (Appendix VI).

Outcomes Analyses

Primary analyses: Comparing the effectiveness of two de-implementation strategies, **Or** vs. **Sc**, on continued low-value ADT use after six months. Our primary outcome is stopping ADT injections, which will likely be evaluated through a combination of chart reviews and informatics data generated through the ordering process. We will also explore the feasibility and impact of six-month outcomes during pilot testing to increase study efficiency and timeliness.

Secondary outcomes: RE-AIM implementation outcomes, changes from baseline measures, total ADT injections per arm at 6 months post implementation. (Table 4). We will examine moderators of strategy effectiveness (e.g., fidelity) and causal mechanisms underlying the strategies through content analysis from study team and pilot site meeting documents and discussion and based on our organizational assessment.

Table 4. Implementation Outcomes (based on the RE-AIM framework)

Domain	Order entry	Script
Reach	$(1 - \# \text{ ADT providers opt out}) / (\text{total ADT providers})$	$(1 - \# \text{ ADT provider opt out}) / (\text{total ADT providers})$

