 - Study staff will work with Site Champions to schedule a virtual IES.
 - The purpose of the IES will be to explain the importance of the study, describe the light touch interventions, and encourage use of the tools provided with the interventions. We will also field questions and address any concerns from providers.
 - The IES will ideally be scheduled during Grand Rounds, tumor boards, or another regularly scheduled clinical department meeting.
 - The IES will be around 10-15 minutes and will include a PowerPoint presentation (see attached).
 - The IES presentation will be tailored to each facility, as needed, and revised based on provider feedback.
 - The Study Co-PI plans to facilitate the IES, but it may also be conducted by study staff or designee chosen by site leadership at their request.
- Confirm List of ADT Providers
 - Once the Site Champions have obtained/provided all necessary approvals/notifications and the IES has been scheduled, study staff will contact the Site Champion and/or department chiefs to confirm the final list of providers in each department who prescribe ADT.
- Intervention Kick-Off
 - Study staff will send providers an email with an attached information sheet and information about the upcoming IES (if IES has not already occurred) (Appendix II).
 - Site Champions will also email providers to encourage participation in the IES (Appendix II).
 - Site Champions will be careful to promote the study at their sites without being coercive.
 - Providers will have a week from the email being sent to opt out. Providers may opt out by emailing the study team at: [contact].
 - Site Champions will not be informed of any providers opting out.
- Ongoing Communications
 - Once the intervention is successfully implemented at the site, study staff will communicate with Site Champions/site staff as needed. These communications may include:
 - Monthly automated email inquiring about any site changes (including changes in providers and procedures), feedback from other staff, or site needs.

- Other communications as needed.
- This pilot work will help us refine our protocol, troubleshoot unforeseen issues in the project, and determine whether our interventions are feasible as designed.
- We will also pilot the preliminary organizational assessment survey by inviting the Site Champions to complete the survey in VA Qualtrics.

IDENTIFYING LOW-VALUE ADT IN PILOT

CDW/CENTRAL CANCER REGISTRY/VITAL STATUS/CMS

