 - Our current plan will be to stratify sites by availability of Radiation Oncology to ensure there is an even distribution of Radiation Oncology in both intervention arms. We intend to randomize sites in blocks of 2-4.
- Once site Clinical Health Information Officer has agreed to implementation the intervention at their site, study staff will apply for site CPRS access.
 - Note: Once you have CPRS access for a site, set an Outlook reminder to log in to each site every 30 days.

TRIAL OR/Sc IMPLEMENTATION

- Implementation procedures will be similar to those of the pilot but refined as needed based on pilot outcomes and needs specific to trial site implementation.
- Interventions will be implemented for up to 12 months at each site.
- Study staff will apply for CPRS access at each site once we receive approval from either the Medical Center Director or Site Champion.
- Baseline ADT Prescribing Meetings – these meetings with Site Champions or their designees will not be mandatory for the RCT. We will move forward with our trial implementation even if we haven't collected information regarding the ADT ordering process.

- Implementation Education Session (IES) – to make scheduling easier on the study team, we may implement one IES per site instead of each department. We will move forward with implementing the interventions after scheduled IES's, even if they have been cancelled.
- There is a possibility that patients will receive ADT injections more than once during the intervention period. If this is the case, then the intervention will be triggered more than once for the same patient.

TRIAL DATA COLLECTION

- Data sources for our primary, implementation and secondary fidelity outcomes will be refined during the pilot. Data collection and outcomes analyses plan will also be further developed during the pilot.
- We will likely assess **Or** fidelity using informatics data generated through the ordering process.
- We will use chart review to identify **Sc** documentation in the EMR, in addition to other informatics approaches.

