- We will match our 4 intervention sites with up to 8 control sites with comparable departments and numbers of patients. We will complete chart reviews for control sites twice. The first review will look at ADT injections at the start of the intervention for the matching intervention site(s) to confirm whether patients would have been eligible at the intervention launch site we are not looking after the date the intervention started. The second review will occur again at the end of the 6-month intervention period for the matching intervention site.
- Providers and Site Champions at participating facilities will be asked to complete anonymous assessments in Qualtrics at baseline and 1-month post-intervention.
- We will examine relationships between survey and trial outcomes in exploratory analyses to assist with understanding the generalizability of our findings.

TRIAL CLINIC AND ADT PROVIDER ASSESSMENTS

- We will obtain national Union review for conducting assessments. For the crRCT, Site Champions and providers will be invited to complete the surveys (Appendix VI). The Ann Arbor Study Team will revise the survey as needed based on piloting feedback and outcomes.

The Site Champion Clinic Assessment

We will administer surveys to our Site Champions upon MCD approval. Survey data will be collected anonymously via VA Qualtrics. The survey includes questions about ADT ordering and clinic practices; the survey should take about 5 minutes to complete.

- We will ask Site Champions to complete a survey at baseline. The exact timing of the survey will be decided during the pilot testing period.

The ADT Provider Assessment

We will administer surveys at baseline and 1-month post-intervention period to ADT prescribers. Survey data will be collected anonymously via VA Qualtrics. The survey includes questions about ADT ordering and clinic practices; the survey should take about 5 minutes to complete.

- Baseline survey - we will ask providers to complete the baseline survey during the IES's. Providers will be able to access the survey by scanning a QR code on their phone (code will be available in the IES PPT), or via a link the study team will enter in the Zoom meeting chat.
- 1-Month post-intervention survey – at the end of the intervention period, we will email providers with a link to the follow up Qualtrics survey.

RECORDS CONTROL AND DISPOSITION

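### The baseline provider survey is an open link at an optional, cancellable education session, so it cannot leave out opted-out providers and draws on a different group from the emailed follow-up

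*Protocol*

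**What the plan says.** All references are to the protocol.

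- **Opt-out (D1.1).** "Opting out means that they will not be asked to participate in surveys or other approaches to measuring provider responses". Under Pilot Site Implementation Overview, providers have one week from the information email to opt out. That email may go out after the IES has been held. Trial procedures are to be similar to the pilot's.
- **Survey population.** The ADT Provider Assessment says: "We will administer surveys at baseline and 1-month post-intervention period to ADT prescribers". The Data collection section says: "an ADT provider assessment will be administered to participating site providers at baseline and 1-month post-intervention through VA Qualtrics". The second wording can mean providers who participate or providers at participating sites.
- **Baseline route (The ADT Provider Assessment).** "we will ask providers to complete the baseline survey during the IES's". On access: "Providers will be able to access the survey by scanning a QR code on their phone", or by a link placed in the meeting chat.
- **Follow-up route (same section).** "at the end of the intervention period, we will email providers with a link to the follow up Qualtrics survey".
- **The session.** "The IES will ideally be scheduled during Grand Rounds, tumor boards, or another regularly scheduled clinical department meeting". The Appendix III provider emails call attendance optional. Trial Or/Sc Implementation adds: "We will move forward with implementing the interventions after scheduled IES's, even if they have been cancelled".
- **The form (Appendix VI).** Three questions, anonymous, none on specialty, prescriber status or opt-out. The Site Champion form does ask specialty.
- **A different plan elsewhere (C1.0).** Selected providers and stakeholders at 20 sites are to be emailed a survey link at baseline and at 6 months.

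**The concern.** There are two separate problems.

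First, D1.1 makes a commitment that the baseline procedure has no means of keeping. A code on a slide or a link in a chat is put to whoever is in the meeting. A provider who has opted out but attends is asked anyway, and an answer from that provider cannot be recognised or removed later.

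Second, the waves are drawn from different frames. Baseline consists of those who came to an optional session. Follow-up is an email list. Where the session is cancelled, no other baseline route is given. Attenders may differ from non-attenders in their attitude to stopping ADT. Without linkage, a difference between waves could reflect who answered as much as any change of mind.

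At stake are the planned exploratory analyses relating survey to trial outcomes, and any use of the provider answers to explain how the strategies work. An analysis plan cannot repair this afterwards, because the identifying information is never collected.

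**Working it through.** **No figure to reproduce.** The protocol states no opt-out rate, IES attendance, response rate, sample size or power for the provider survey. The check is mainly textual.

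**Step 1: compare the routes.**

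| | Baseline | Follow-up |
|---|---|---|
| How providers are asked | QR code or chat link in the IES | Emailed link |
| Who can be reached | Those attending | Those on the mailing list |
| Opt-out filter stated | None; the open route cannot apply one | None; a mailing list could apply one |
| If the IES is cancelled | No stated route | Unaffected |
| Linked to the other wave | No | No |

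**Step 2: order of events.** The IES may precede the opt-out email, so a provider can be surveyed before being offered the opt-out. That does not breach D1.1, but it means the baseline group cannot be defined as prescribers who did not opt out.

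**Step 3: can it be corrected later?** No. The form has no item separating opted-out or non-prescribing respondents, and no code pairs the waves.

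**Step 4: illustration, all inputs assumed.** Suppose nobody's opinion changes.

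*Attendance.* Let *g* be the share of follow-up respondents who never attended the IES, and *D* the absolute difference between their mean and that of attenders on a 5-point item. The apparent shift is *g* × *D*.

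| *g* | *D* = 0.25 | *D* = 0.5 | *D* = 1.0 |
|---|---|---|---|
| 0 | 0 | 0 | 0 |
| 0.2 | 0.05 | 0.10 | 0.20 |
| 0.4 | 0.10 | 0.20 | 0.40 |
| 0.6 | 0.15 | 0.30 | 0.60 |

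*Opt-out.* Let *f* be the share of baseline respondents who opted out and are absent at follow-up, with *D* now the difference between them and the rest. The apparent shift is *f* × *D*.

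| *f* | *D* = 0.25 | *D* = 0.5 | *D* = 1.0 |
|---|---|---|---|
| 0 | 0 | 0 | 0 |
| 0.05 | 0.013 | 0.025 | 0.05 |
| 0.10 | 0.025 | 0.05 | 0.10 |
| 0.20 | 0.05 | 0.10 | 0.20 |

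Both ranges start at zero, and *D* can have either sign. On these assumptions attendance could matter more than opt-out.

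**The case against.** A reader might infer that the baseline goes to everyone in the room, that the least willing prescribers are therefore in the baseline and missing at follow-up, and that attitudes will appear to improve when nobody has changed. The protocol does not support that chain.

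- It says providers are asked, and it names ADT prescribers as the population for both waves. That non-prescribers answer at Grand Rounds or a tumor board is possible but not planned.
- It does not say that the follow-up email leaves out opted-out providers. If D1.1 is applied to both waves they are in neither; if to neither, they are in both. An opt-out contrast arises only if the list is filtered and the open link is not.
- The Appendix III kick-off email, which carries the IES invitation, tells anyone who has opted out to ignore it. Opted-out prescribers may well be the least likely to attend.
- The IES is meant to encourage use of the tools, which could move answers given during it. The protocol does not say at what point in the session the survey is taken, so this effect is also unknown.

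Nor is it fair to say that the plan breaks its promise outright. A breach needs a provider who has already opted out, attends anyway and is shown the link.

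It can also be said that this is a short anonymous survey in a 4-site pilot trial with exploratory use, and that no before/after survey measure is clearly defined. The secondary outcome on changes from baseline is not tied to the survey. All of this stands, and it limits the severity. It does not answer the two remaining facts: the baseline route cannot honour D1.1, and the two waves have different frames that cannot be reconciled afterwards.

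**Conclusion.** The point holds in a limited form and is minor. As written, the baseline procedure cannot exclude opted-out providers. It samples IES attenders only, or no one where the session is cancelled, while follow-up samples an email list. Because the answers are anonymous, unlinked and carry no prescriber or opt-out item, a before/after comparison may be biased and this cannot be checked. The protocol fixes neither size nor direction; the 0 to 0.60 point range rests wholly on assumed shares and differences, and zero is consistent with the text. The primary outcome, stopping ADT injections, comes from chart review and ordering data and is not touched.

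**What to change.** 1. Email both waves to the same confirmed list of ADT prescribers, minus opt-outs. C1.0 already describes emailed invitations at both waves.
2. Open the baseline after the one-week opt-out window and close it before the IES. Remove the QR code and chat link.
3. Add an anonymous self-generated code so that a respondent's two answers can be paired. This also deals with providers who withdraw in between, which D1.3 allows. Otherwise, report the waves as separate cross-sections, as should be done wherever a baseline has already been collected at the session.
4. Limit before/after summaries to sites with both waves. The printed form has no site item, so this needs a separate link per site unless the links are already site-specific.
5. Reconcile C1.0 (emailed; baseline and 6 months; 20 sites), D1.1, Data collection and The ADT Provider Assessment on who is surveyed, how and when.

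The cost is a protocol modification, which D1.1 sends to the Research & Development Committee, and one additional email per site. Baseline response may be lower than at a live session, and every IES would have to follow the opt-out week, which the present procedure does not require.
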